Validation of Serum Assays for the Diagnosis of Gastritis

ClinicalTrials.gov ID: NCT05883345

Document date: May 28, 2023

Main investigator

Name: [name], PhD

Address: [name]

Phone/[contact]

E-mail: [contact]

Number of involved center: 1 (Konkuk University Medical Center)

Title of the study: Validation of Blood Test Finding for the Diagnosis of Gastritis and Gastric Neoplasms

Protocol ID: 2023-04-056

Keywords: *Helicobacter pylori*, Atrophic gastritis, Gastric cancer, Pepsinogen

Rationale of the study

Helicobacter pylori-seropositive rates are decreasing in South Korea. Seroprevalence was 74.3% in 1990, but it decreased to 43.9% in 2016. In Koreans, most gastric cancers are related to *H. pylori* infection. *H. pylori*-negative gastric cancers were found only in 2.3% among the 1,833 Korean gastric cancer patients. Despite these facts, the national guideline still recommends biennial gastroscopy for all Koreans aged between 40 and 75 years. Therefore, 8,462,570 (63.1%) Koreans underwent gastric cancer screening among the target population of 13,404,927 individuals in 2021.

In *H. pylori*-seroprevalent populations, diagnostic criteria for naive status should be strict based on histology, endoscopy, and serum pepsinogen (PG) assay findings. Naive condition should be diagnosed only when both invasive and non-invasive *H. pylori* tests show negative

findings. Furthermore, there should be no intestinal metaplasia and atrophy on serum PG assay, endoscopy, and histology findings in *H. pylori*-naive participants. Based on those findings, *H. pylori* infection will be confirmed when invasive tests or urea breath test was positive. *H. pylori*-naive status will be diagnosed if there was no eradication history, no serologically detected atrophy (PG I \leq 70 ng/mL and PG I/II \leq 3), and no intestinal metaplasia or atrophy on endoscopy and histology.

This study aimed to determine the validity of blood tests for gastric cancer screening according to the *H. pylori* infection status. We tried to identify significant variables using GastroPanel tests and traditional serum PG assays according to the presence gastric neoplasms.

Study design

Study Type	Observational
Observational Study Model	Cohort
Time Perspective	Prospective
Biospecimen Retention	Samples Without DNA
Biospecimen Description	Blood sample
Enrollment	1490 [Actual]

Primary objective: To determine the validity of blood tests for gastric cancer screening

Endpoints:

- Primary endpoint: Significant blood test findings (*H. pylori* IgG, PG I, PG II, I/II ratio, G-17) indicating the presence of gastric neoplasms
- Secondary endpoint: Test findings according to the types of gastric neoplasms

Expected results: GastroPanel test and conventional serum pepsinogen findings would differ according to the presence and types of gastric neoplasms.

Analyzed criteria: Gastric neoplasms were diagnosed when microscopic findings correspond to the international classification of diseases-10 categories C16, D002, D131, and C1884. Adenocarcinomas (C16 and D002) were further divided into advanced gastric cancers (AGCs) and early gastric cancers (EGCs) after resecting the cancers. Gastric adenomas were confirmed among benign neoplasms of the stomach (D131), after the resection. Following excision of submucosal tumors, neuroendocrine tumors (NETs) and gastrointestinal stromal tumors (GISTs) were verified as C16. Primary gastric mucosa-associated lymphoid tissue (MALT) lymphomas were identified as C1884 using the gastric biopsy specimens.

Main variables/endpoints of the analysis

Age (years)
Male sex
Status of H. pylori infection
GastroPanel test findings H. pylori IgG (EU) PG I (µg/L) PG II (µg/L) I/II ratio Gastrin-17 (pmol/L)
Conventional serum assays (Chorus tests and HBI PG assays) H. pylori IgG (AU/mL) PG I (mg/dL) PG II (mg/dL) I/II ratio

Safety variables: No adverse events during the study period (May 1, 2023 ~ August 30, 2024)

Visits and examinations

Initial visit:

- Blood test for *H. pylori* immunoglobulin G, pepsinogen, and gastrin-17 levels
- Upper gastrointestinal endoscopy and gastric biopsy

Follow-up visit:

- ¹³C-urea breath test if there is a discrepancy between the *H. pylori* test findings

Study population

Short description of the main inclusion and exclusion criteria

Study Population:	Adult population who visited our center for gastric cancer screening using serum assays
Sampling Method:	Non-Probability Sample
Minimum Age:	18 Years
Maximum Age:	99 Years
Sex:	All
Gender Based:	No
Accepts Healthy Volunteers:	No

Criteria:	
Inclusion Criteria:
 
 • Individuals who visited for gastric cancer screening 
Exclusion Criteria:
 
 • History of gastrectomy • Renal insufficiency • Severe comorbidities requiring prompt management
-----------	--

Sample size and statistical analysis

Prior to the study, sample size calculation was done for the validation of GastroPanel test in Koreans. Briefly, two-sided tests were used at a significance level of 0.05. Using PASS 2023 (NCSS, LLC. Kaysville, Utah, USA), the power was 0.842 when 414 individuals are included.

Chi-square test was used for categorical variables, while t-test was used for continuous variables to compare the differences between the patients with gastric neoplasms and the controls. When the data showed asymmetrical distribution, Fisher's-exact was used to present categorical variables as proportion, while Kruskal-Wallis test was used to present continuous variables as median value with ranges. ANOVA with Bonferroni correction was used to assess differences between the three groups for continuous variables, while chi-square test with Bonferroni correction was used for categorical variables. Thereafter, independent variables for gastric neoplasms were identified using logistic regression analysis. The results are shown as odds ratio (OR) with 95% confidence intervals (CIs). Correlation analysis was used to identify associations between the blood test results and the severity of

atrophy. The results are shown as correlation coefficient (r) values. Furthermore, receiver operating characteristic (ROC) curve analysis was done, and presented as area under the curve (AUC). ROC curves were compared using the McNemar's test. Using PASW statistics (version 28.0; SPSS Inc., Chicago, IL, USA), a p -value less than 0.05 was considered significant.

Duration of the study

Study Start:	May 1, 2023 [Actual]
Primary Completion:	August 30, 2024

Additional features on the main concept of the study

Serum pepsinogen (PG) assays are another method used to quantify the severity of atrophy, in addition to endoscopic and microscopic measurements. In contrast to traditional serum PG assays, GastroPanel tests incorporate the measurement of gastrin-17 (G-17), a substance exclusively secreted by the gastric antrum. The G-17 level decreases to less than 1 pmol/L following distal gastrectomy or in the presence of antral atrophy, but it increases to 30 pmol/L when corpus atrophy develops. European studies using GastroPanel tests revealed that gastric atrophy can be identified with low G-17 levels of <1 pmol/L. Nonetheless, this metric is difficult to apply in *H. pylori*-seroprevalent areas where corpus atrophy is common. A Chinese study showed that gastric cancer development is linked to both low (<0.5 pmol/L) and high (>4.7 pmol/L) G-17 levels; however, these are less helpful in clinical practice because G-17 levels of >4.7 pmol/L are frequently observed even in the absence of atrophy. Altogether, it is still uncertain whether adding a G-17 measurement to PG assays would contribute to the detection of gastric neoplasms. Hence, we attempted to identify actual blood levels for

detecting gastric neoplasms rather than focusing on identifying high-risk individuals.

Additionally, we tried to confirm the significance of the test results according to the type of gastric neoplasm.

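### Five primary markers (nine readouts) are each tested at p<0.05 with no lead marker, primary platform or cross-marker correction, so the chance of at least one false-positive primary finding is about 20-30% if none is related to neoplasm

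*Combined protocol and SAP*

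**What the plan says.** The primary endpoint, under Endpoints, is "Significant blood test findings (*H. pylori* IgG, PG I, PG II, I/II ratio, G-17) indicating the presence of gastric neoplasms". No marker leads, no order of testing is given, and nothing says how many markers must reach significance.

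Main variables/endpoints of the analysis lists five GastroPanel readouts, the last of them being gastrin-17. Under "Conventional serum assays (Chorus tests and HBI PG assays" it lists four more: IgG, PG I, PG II and the ratio. The Rationale confirms that both platforms enter the neoplasm comparison: "We tried to identify significant variables using GastroPanel tests and traditional serum PG assays according to the presence gastric neoplasms".

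Under Sample size and statistical analysis, patients with neoplasms are compared with controls by chi-square or t-test, with Fisher's exact or Kruskal-Wallis for asymmetrical data. Logistic regression follows, and then ROC analysis. The only threshold is that "a p -value less than 0.05 was considered significant". The only multiplicity correction is for three groups: "ANOVA with Bonferroni correction was used to assess differences between the three groups for continuous variables", with the same for categorical variables by chi-square.

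**The concern.** The stated primary objective is to determine the validity of the blood tests for cancer screening, so a marker reported as indicating neoplasm will be read as a confirmed result. With five markers, four of them read twice, and each test at 0.05, the set as a whole does not have a 5% error rate. The plan corrects for multiplicity between three groups but not across the markers that make up its primary claim.

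There is also a problem of reading. If PG I, say, reaches significance on one platform and not on the other, the plan does not say which result counts, so either could be reported. G-17 is exposed in a different way. The closing section calls its added value uncertain, and that is the kind of question on which a chance finding could be taken as an answer.

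**Working it through.** **The plan's own figure.** The only figure is power 0.842 with 414 individuals, two-sided 0.05. It cannot be reproduced, because no effect size, SD, rates or group ratio is given. Back-solving the two-means formula gives an implied standardized difference of 0.291 with 1:1 groups, 0.364 with 20% cases and 0.485 with 10% cases. These are implied values, not a check.

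**Inputs from the documents.** Five markers; five GastroPanel readouts plus four conventional ones = nine; 0.05 per test; enrollment 1,490.

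**Inputs assumed.** The documents give no correlation between markers or platforms and no case share, so ranges are used.

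**Chance of at least one false positive when no marker is related**

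- Independent tests: 1 - 0.95^5 = 0.226; 1 - 0.95^9 = 0.370.
- Correlated test statistics (1,000,000 draws; log ratio taken as log PG I minus log PG II; PG I with PG II 0.3-0.7; between platforms 0.70-0.95): 0.196-0.207 for five and 0.234-0.298 for nine.
- Simulated participants (1,490, 10% cases, cross-platform reliability 0.80-0.95, log PG I with log PG II 0.5-0.7; 4,000 replicates per setting): 0.197-0.218 for five and 0.247-0.300 for nine.
- Extreme case, every pair of readouts correlated 0.95: 0.085 for five and 0.098 for nine.

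**Chance that one given unrelated marker is declared significant**

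- One platform (G-17): 0.05.
- Either of two platforms: 0.078 at correlation 0.80, 0.070 at 0.90, 0.065 at 0.95; at most 1 - 0.95^2 = 0.0975.

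**Some markers truly related.** Suppose the pepsinogen markers are related, and IgG (two platforms, correlation 0.80-0.95) and G-17 are unrelated and independent of each other. The rate is 1 - (1 - 0.065)(0.95) = 0.11 to 1 - (1 - 0.078)(0.95) = 0.12. If only G-17 is unrelated, it is 0.05.

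**With the correction.** Five markers on one platform at 0.05/5 = 0.01: 1 - 0.99^5 = 0.049 if independent, and 0.044-0.053 in the simulation of participants (values above 0.05 are within simulation error).

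**Power at the strictest Holm level (0.01), taking 0.842 at 414 as given**

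- Noncentrality at 414: 1.960 + 1.003 = 2.963. Power at 414: Φ(2.963 - 2.576) = 0.65. To keep 0.842 at the same effect and case share: 414 × ((2.576 + 1.003)/2.963)^2 ≈ 604.
- At 1,490, same effect and case share: 2.963 × sqrt(1490/414) = 2.963 × 1.897 = 5.62; power 0.999.
- At 1,490, if the calculation assumed 1:1 groups (difference 0.291) and 10% are cases: 0.2912 × sqrt(149 × 1341/1490) = 3.37; power 0.79, against 0.92 at 0.05.
- The same with 5% cases: 0.2912 × sqrt(74.5 × 1415.5/1490) = 2.45; power 0.45, against 0.69 at 0.05.

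**The case against.** The best defence is that this is a marker-by-marker search in an observational, non-probability sample. The plan nowhere says that one significant marker is enough, and some statisticians would not require family-wise control in such a setting. This stands in part. That any marker will do is an inference from the absence of a success rule, and labelling the search exploratory would be an honest alternative. It does not remove the point, because the plan calls these findings its primary endpoint and ties them to screening validity.

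The all-null case is also the worst case. The Rationale links most Korean gastric cancers to *H. pylori*, so IgG at least may well be related to neoplasm, and the family-wise rate then falls. This stands too.

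A reader might infer several stronger things that the documents do not support:

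- That an unrelated marker is declared significant far more often than 5% of the time. That is a per-marker rate, and it stays at 5% for G-17 and below 10% for any marker on two platforms. What is inflated is the chance of at least one false finding in the set.
- That 37.0% is an estimate. It treats two assays of the same analyte as independent, so it is a ceiling.
- That having both a two-group test and a regression raises the rate further. The regression comes after the two-group test. If both must be significant, the rate could fall. The text does not settle this.
- That the 0.842 power is wrong. It cannot be checked, and it may not concern a neoplasm contrast at all, since the plan says only that it was for validating GastroPanel in Koreans.

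The Bonferroni correction in the plan is not an answer, because it covers comparisons between three groups, not the family of markers in the comparison of neoplasms with controls.

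**Conclusion.** The concern holds for the family of primary tests and not for any single marker. If none of the markers is related to neoplasm, the chance of at least one false-positive primary finding is about 20-22% for five markers and 23-30% for nine readouts. These figures rest on assumed correlations. Near-perfect correlation among all readouts would bring them below 10%, which is still above 5%. They also assume that one significant marker would be reported as a primary finding, which the plan leaves open. The lack of an agreed reading when the two platforms disagree needs no such assumption. This is worth fixing because the fix is cheap. It does not undermine the study.

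**What to change.** In Sample size and statistical analysis, add a few sentences that:

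1. name GastroPanel as the primary platform, since the sample size was calculated for it, with the conventional assays secondary;
2. name one deciding analysis per marker;
3. apply Holm across the five primary markers;
4. report unadjusted p-values and 95% confidence intervals for everything else as supportive.

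The documents list 1,490 as actual enrollment and describe the analyses in the past tense, but do not show whether results had been seen. If they had been when this is set, report the Holm-adjusted p-values and describe the choice of platform as post hoc. Naming it late does not by itself restore error control.

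No new data are needed. The cost is power per marker, and its size depends on the case share and effect size, which the plan should state. With 1,490 participants it is negligible if the sample-size calculation used the cohort's actual case share. It is material if that calculation assumed equal groups and cases are few.

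### Does the small number of H. pylori-negative cancers expected among 1,490 participants undermine the aim of assessing blood tests by H. pylori status?

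*Combined protocol and SAP*

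**What the plan says.** Under Rationale of the study, the aim is worded by infection status: "This study aimed to determine the validity of blood tests for gastric cancer screening according to the *H. pylori* infection status". The same section reports that H. pylori-negative "gastric cancers were found only in 2.3% among the 1,833 Korean gastric cancer patients", and observes that "the national guideline still recommends biennial gastroscopy for all Koreans aged between 40 and 75 years". Its definition of H. pylori-naive status requires no eradication history, no serological atrophy (cut-offs PG I 70 ng/mL and PG I/II ratio 3) and "no intestinal metaplasia or atrophy on endoscopy and histology". Study design gives actual enrolment as 1,490.

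The Primary objective is worded without the by-status phrase: "To determine the validity of blood tests for gastric cancer screening". The primary endpoint concerns blood findings that indicate gastric neoplasms, and the secondary endpoint concerns findings by neoplasm type. H. pylori status appears in the list of main variables.

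Under Sample size and statistical analysis, the reader learns that a "sample size calculation was done for the validation of GastroPanel test in Koreans", at two-sided 0.05, and that "the power was 0.842 when 414 individuals are included". Effect size, endpoint, case fraction and test are not given. The planned methods are comparisons of neoplasm patients with controls, a three-group comparison ("ANOVA with Bonferroni correction was used to assess differences between the three groups for continuous variables", groups not named), logistic regression, correlation with atrophy severity, and ROC curves. None is specified within H. pylori strata.

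**The concern.** The rationale combines falling seroprevalence, the rarity of H. pylori-negative cancer and a guideline that still covers everyone in the age range. Read that way, uninfected people look like the group the study is really about. If only about one cancer in forty arises in them, a single-centre screening cohort will contain very few such cases, and the 414-person calculation says nothing about them.

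Two misreadings would then be possible. A result within H. pylori-negative participants, significant or not, might be taken as evidence for or against blood-test screening in them when it rests on a few cases. Or a pooled AUC or odds ratio might be applied to them although about 98% of the gastric cancers behind it would be H. pylori-related.

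**Working it through.** **The plan's own figure.** Power of 0.842 at 414 cannot be reproduced, because the effect, test and case fraction are missing. Solving backwards for a two-sided comparison of means, power ≈ Φ(d/√(1/n₁ + 1/n₂) − 1.96), it is reached with:

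- d = 0.29 for 207 against 207;
- d = 0.49 if 10% are cases;
- d = 0.67 if 5% are cases.

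Many designs fit, so the figure is neither confirmed nor contradicted.

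**Inputs for the count by status.** The H. pylori-negative share of cancers is 2.3% of 1,833 (0.023 × 1,833 ≈ 42; Wilson 95% CI about 1.7% to 3.1%). Enrolment is 1,490. The cancer yield is not in the documents, so 1% to 20% is assumed.

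Expected H. pylori-negative cancers = 0.023 × C, where C is the number of cancers. The chance of none is 0.977^C.

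| Assumed yield | C | Expected at 2.3% | Expected at 3.08% | Chance of none |
|---|---|---|---|---|
| 1% | 15 | 0.3 | 0.5 | 0.71 |
| 5% | 74 | 1.7 | 2.3 | 0.18 |
| 10% | 149 | 3.4 | 4.6 | 0.03 |
| 20% | 298 | 6.9 | 9.2 | 0.001 |

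Expecting five needs 5/0.023 ≈ 217 cancers, 14.6% of those enrolled. Expecting ten needs 435, or 29.2%.

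**What such counts can show.** Exact 95% intervals for sensitivity are 29% to 100% for 3 of 3 and 29% to 96% for 5 of 7. For an AUC of 0.70 (Hanley–McNeil), taking about 836 seronegative participants (1,490 × (1 − 0.439), assuming the 2016 seroprevalence applies), the 95% half-width is 0.33 with 3 cases and 0.22 with 7. So the subgroup would be very imprecise.

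**The comparison the plan does specify.** With all 1,490 participants, the same formula at AUC 0.70 gives a half-width of 0.068 with 74 cases and 0.049 with 149. The small negative stratum does not weaken this.

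**Does 2.3% fit the endpoint?** Only partly. The endpoint is gastric neoplasms: adenocarcinoma, adenoma, neuroendocrine and stromal tumours, and MALT lymphoma. The documents give no H. pylori-negative share for the non-cancer types, nor the definition of negative used by the cited series. The number of negative cases in the planned analyses therefore cannot be derived.

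**Would a formal naive-only accuracy report help?** Naive participants are defined partly by not meeting the serological atrophy criterion. Pepsinogen sensitivity at that cut-off is therefore zero among them by construction, and the pepsinogen AUC is computed over a restricted range. More cases would not cure this, and an exact interval would present a definitional result as sampling error.

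**The case for a change.** The strongest argument for a change is that the by-status aim is written down and never withdrawn, H. pylori status is a main variable, and the remedy would cost only a scope sentence and a column of counts. The arithmetic behind it is correct: five or fewer H. pylori-negative cancers are expected at any yield up to about 14.6%. It is also true that the rationale and the primary objective word the aim differently, and that no by-status analysis is named.

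What stands is a difference in wording and a warning about interpretation. The rest does not carry a change:

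- A restriction on conclusions in H. pylori-negative people would withdraw a claim the plan does not make. The rationale's next sentence, the endpoints, the expected results and the closing section all return to the presence and type of neoplasm.
- It might be argued that the group could never supply enough cases, since 0.023 × 1,490 ≈ 34 even if every participant had cancer, while estimating 70% sensitivity to within 15 points needs 40. But 34 is an expected value, not a maximum. At the 3.08% limit it becomes 0.0308 × 1,490 ≈ 46, and the 15-point target is not the plan's.
- The missing inputs to the 414 calculation are a gap in reporting. Supplying them would change no planned analysis.

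**Conclusion.** No change to the plan follows. If cancer yield lies between 1% and 20%, which is an assumption, about 0.3 to 7 H. pylori-negative cancers are expected, or up to about 9 at the upper limit of the 2.3% figure. That is low precision in a subgroup for which the plan specifies no analysis, power or conclusion. The stated power is not shown to be wrong, and the overall comparison of neoplasms with controls is not shown to be underpowered.

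The difference between the two statements of the aim is one that analysts resolve sensibly by following the stated objective and endpoints. Anyone tabulating results by H. pylori status will see the case counts and wide intervals and treat them as descriptive. Adding those counts to a table would alter no estimate. A formal accuracy claim in naive participants would gain nothing for pepsinogen, because the naive definition already fixes the answer at its own cut-off.

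This rests on reading the objective and endpoints as governing. It would be different if a report drew a validity conclusion specifically for H. pylori-negative people, which the plan does not propose.

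### The plan makes no provision for unequal variances: the t-test version is unstated and the three-group ANOVA is the classical one, so the 0.05 level is not protected if group sizes and spreads both differ

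*Combined protocol and SAP*

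**What the plan says.** Under Sample size and statistical analysis, the two-group rule is that a "t-test was used for continuous variables to compare the differences between the patients with gastric neoplasms and the controls". For the wider comparison, "ANOVA with Bonferroni correction was used to assess differences between the three groups for continuous variables". Which three groups are meant is not stated. The level is set twice: "two-sided tests were used at a significance level of 0.05" for the sample size, and "a p -value less than 0.05 was considered significant" for the analysis.

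The only fallback opens with "When the data showed asymmetrical distribution"; for continuous markers, "Kruskal-Wallis test was used to present continuous variables as median value with ranges". Unequal variance is not a trigger, and the section does not say whether the t-test is the pooled or the Welch version. Logistic regression and ROC analysis follow.

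The primary endpoint asks which of five blood findings (*H. pylori* IgG, PG I, PG II, their ratio, G-17) are significant for neoplasm. The one remark that bears on spread is in the closing background section, which reports from a cited study that "gastric cancer development is linked to both low (<0.5 pmol/L) and high (>4.7 pmol/L) G-17 levels".

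**The concern.** A pooled-variance test estimates one SD from everyone. If one group is much larger, that SD is essentially the larger group's. The standard error of the difference, however, is driven by the smaller group. If the smaller group is more variable, the standard error is too small and false positives rise; if it is less variable, the test becomes too strict and loses power. This also happens with symmetric or log-transformed data, so the asymmetry rule does not catch it. Bonferroni does not repair it either: it moves the threshold from 0.05 to 0.05/3 and leaves the standard error unchanged.

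The conditions are plausible here. People attending for screening probably include a minority with neoplasm. A marker that moves both down and up in cases, as the background section suggests for G-17, could show little mean difference but a wider spread. Whether G-17 adds anything is the study's own open question, and a pooled test could report a mean difference that is not there.

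**Working it through.** **The plan's own figure.** The section says "the power was 0.842 when 414 individuals are included", but gives no effect size, SD, allocation or test, so this can be neither reproduced nor refuted. For a comparison of two means it implies a standardised difference of 0.291 at a 1:1 split, 0.485 with 10% cases and 0.668 with 5%. It says nothing about variances.

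**Inputs from the document.** N = 1,490 enrolled (Study design); two-sided level 0.05.

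**Assumptions.** Case share 2, 5, 10, 20 or 50%; case-to-control SD ratio r of 0.67, 1, 1.5 or 2; normal data; no true mean difference; t-test read as pooled.

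**Formula.** With the control SD set to 1, n1 cases and n2 controls:

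- sp² = [(n1 − 1)r² + (n2 − 1)] / (n1 + n2 − 2)
- V_pooled = sp²(1/n1 + 1/n2)
- V_true = r²/n1 + 1/n2
- type I error = 2[1 − Φ(1.96 √(V_pooled / V_true))]

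**One case in full (74 cases, 1,416 controls, r = 1.5).** sp² = (73 × 2.25 + 1,415)/1,488 = 1.0613. V_pooled = 1.0613 × 0.014220 = 0.01509. V_true = 2.25/74 + 1/1,416 = 0.03111. The variance ratio is 0.485 and its root 0.6965, so the effective critical value is 1.96 × 0.6965 = 1.365 and the error is 0.172.

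**Pooled t-test, type I error:**

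| Cases / controls | r = 0.67 | r = 1 | r = 1.5 | r = 2 |
|---|---|---|---|---|
| 30 / 1,460 | 0.004 | 0.050 | 0.184 | 0.310 |
| 74 / 1,416 | 0.005 | 0.050 | 0.172 | 0.285 |
| 149 / 1,341 | 0.007 | 0.050 | 0.154 | 0.246 |
| 298 / 1,192 | 0.013 | 0.050 | 0.121 | 0.179 |
| 745 / 745 | 0.050 | 0.050 | 0.050 | 0.050 |

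Simulation (20,000 runs per cell) agrees to about 0.005. Welch's t-test stays between 0.046 and 0.055 throughout.

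**Power when cases are less variable.** With 74 cases and r = 0.67, √(V_pooled/V_true) = 1.429, so the pooled test in effect uses 1.96 × 1.429 = 2.80 true standard errors. A difference that Welch detects with 79% power lies about 2.77 standard errors from zero (1.96 + 0.81). The pooled test detects it with probability Φ(2.77 − 2.80), about 49%.

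**Three groups (40,000 simulated runs; both smaller groups have SD ratio r to the largest; splits assumed):**

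| Group sizes | r | Omnibus ANOVA | Any Bonferroni pair | Welch ANOVA |
|---|---|---|---|---|
| 1,341 / 75 / 74 | 1.5 | 0.213 | 0.191 | 0.048 |
| 1,341 / 75 / 74 | 2 | 0.361 | 0.331 | 0.050 |
| 497 / 497 / 496 | 1.5 | 0.054 | 0.047 | 0.052 |
| 497 / 497 / 496 | 2 | 0.054 | 0.050 | 0.049 |

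**Do the other planned analyses protect the result?** These checks used 4,000 simulated runs with 75 cases of 1,490. The ordinary Wald test of a single linear marker term in logistic regression had error 0.168 at r = 1.5 and 0.300 at r = 2, the same as the pooled t-test in those runs. Kruskal-Wallis gave 0.096 and 0.142. Brunner-Munzel gave 0.046 and 0.051. A sandwich standard error in the logistic model reduced the error to 0.058 and 0.076; with only 30 cases it was 0.075 and 0.089.

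**The case against.** A reader might infer that the plan pools one variance across a small neoplasm group and a very large control group, and that the significance test behind the primary endpoint is therefore wrong. The documents do not support that, for these reasons, all of which stand:

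- The word t-test leaves the version open. Welch's test may be what was meant.
- No case count is given. Imbalance is plausible in a screening cohort but assumed, and at a 50:50 split the pooled t-test keeps its level.
- No marker SD is given. The remark about low and high values concerns G-17 alone, comes from a cited study, and does not establish that cases are more dispersed. The same sentence adds that high values are common without atrophy. For the other four markers there is no evidence on spread.
- The ANOVA sentence is not tied to neoplasm versus control. The study's aim also refers to *H. pylori* status, so the three groups may be something else. With near-equal groups the error is about 5%.
- G-17 is described as running from below 1 to 30 pmol/L. If judged asymmetrical it would go to Kruskal-Wallis, and the t-test figures would not apply.

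Two defences do not hold fully. The Kruskal-Wallis fallback helps only in part: across 30 to 150 cases and the same two wider SD ratios its error is roughly 9 to 16%. Logistic regression gives no protection in its ordinary form, because the single-marker Wald test has nearly the same error as the pooled t-test. It is true, however, that the plan does not say which analysis decides the primary endpoint, so these comparisons cannot be called its sole basis.

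**Conclusion.** The point holds as a conditional weakness. What is certain from the text is that the t-test version is unstated, the three groups are undefined, and nothing in the section deals with unequal variance. Classical ANOVA pools; the t-test does so if read in its standard form. Any loss of the 0.05 level needs unequal group sizes and unequal spreads together. The 12 to 18%, 18 to 31% and roughly 1% figures rest on an assumed case share of 2 to 20%, assumed SD ratios and normal data; they show what could happen and do not estimate what did. The true direction could be liberal, conservative or neither, and may differ between markers. It is worth acting on because the plan has no safeguard and one is nearly free. Label: cheap improvement, conditional on unequal spread.

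**What to change.** In Sample size and statistical analysis:

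1. Name Welch's t-test for neoplasm patients versus controls.
2. Replace the classical ANOVA by Welch ANOVA, with Games-Howell or Bonferroni-adjusted Welch pairwise tests, and define the three groups.
3. Use these by default, without a preliminary test of variances.
4. Where a rank comparison is used, judge it by the nonparametric 95% CI of the AUC or by the Brunner-Munzel test.
5. Use robust standard errors for marker terms in the logistic model. With very few cases these remove most of the excess error but not all of it, so report the number of cases beside the result.
6. State which analysis decides the primary endpoint.

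The cost is a change of wording and, if the classical tests have already been run, a rerun on the same data. No new data are needed. The downside is a negligible loss of power if the variances are in fact equal.
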